6.0 PATIENT POPULATIONS**6.1 ENROLLED POPULATION**

The Enrolled Population will consist of all patients who signed the informed consent and receive a participant ID number.

6.2 SAFETY POPULATION

The Safety Population will consist of all patients in the Enrolled Population who received at least 1 dose of study treatment. The safety analysis will be based on the actual treatment assigned.

This population will be used for all analyses unless otherwise specified.

7.0 PATIENT DISPOSITION

Disposition will be summarized by the number and percentage of patients in each treatment group separately for each phase. The total number of patients screened will be summarized.

Screen-failure patients (i.e., patients screened but not enrolled) and the associated reasons for fail to enroll will be tabulated for the all screened patients. The number and percentage of patients who complete each study phase (Phase 1 or 2a) and patients who prematurely discontinue during the same period will be presented for each treatment group and pooled across treatment groups separately for each phase. The reasons for premature discontinuation from the corresponding study phases will be summarized (number and percentage) by treatment group separately for each phase. All patients who prematurely discontinue during the corresponding study phases will be listed by discontinuation reason.

8.0 DEMOGRAPHICS AND OTHER BASELINE CHARACTERISTICS

Demographic parameters (age; age group; race; ethnicity; sex), baseline characteristics (weight; height; and body mass index, calculated as weight [kg]/(height [m])²) will be summarized descriptively by treatment group separately for each phase.

The number and percentage of patients with medical histories in each system organ class and preferred term will be summarized by treatment group separately for each phase. In addition, ocular medical history will be summarized for the study eye by treatment group separately for each phase.

Concurrent procedure is defined as any procedure performed on or after the date of the first dose of study treatment. The number and percentage of patients with concomitant procedures in each system organ class and preferred term will be summarized by treatment group separately for each phase. In addition, ocular medical history will be summarized for the study eye by treatment group separately for each phase.

Medical histories and concomitant procedures will be coded using the MedDRA, version 21.0 or newer.

Prior medication is defined as any medication taken before the date of the first dose of study treatment. *Concomitant medication* is defined as any medication taken on or after the date of the first dose of study treatment. The World Health Organization (WHO) Drug Dictionary Enhanced will be used to classify prior and concomitant medications by therapeutic class and drug name.

The number and percentage of patients with prior medications will be summarized under each drug class and drug name by treatment group separately for each phase. A separate summary for prior ocular medications used in the study eye under each drug name by treatment group separately for each phase. If a patient took a specific medication multiple times or took multiple medications within a specific therapeutic class, that patient would be counted only once for the coded drug name or therapeutic class. Formulations (including salts, esters, etc.) containing the same active ingredient will be pooled under the coded drug name of the base compound. Medications containing multiple active ingredients of different coded drug names will be reviewed during the course of the study and may be pooled under a single coded drug name for analyses.

Similarly, the number and percentage of patients with concomitant medications will be summarized under each drug class and drug name by treatment group separately for each phase separately for Core Study Visits and Long-term Follow-up Visits. A separate summary for concomitant ocular medications used by eye (study eye and fellow eye) under each drug name by treatment group separately for each phase separately for Core Study Visits and Long-term Follow-up Visits.

9.0 EXTENT OF EXPOSURE AND TREATMENT COMPLIANCE**9.1 EXTENT OF EXPOSURE**

Number and percent of patients exposed to the study treatment will be summarized by treatment group separately for each phase.

9.2 MEASUREMENT OF TREATMENT COMPLIANCE

This is a single dose study and thus treatment compliance is not applicable.

10.0 EFFICACY ANALYSES

All analyses will be based on the observed data. *Baseline* for efficacy is defined as the last non-missing efficacy assessment before the first dose of study treatment. All confidence intervals will be 2-sided 95% confidence intervals, unless stated otherwise.

The efficacy parameter will be the change from baseline VA, full field sensitivity, ambulation, object detection discrimination, VEP, ERG, QoL (composite score of NEI VFQ-25 scores) for the study eye at the scheduled Post-treatment visits and will be summarized by visit and by treatment group separately for each phase.

The NEI-VFQ-25 consists of 25 vision-targeted questions that represent 11 vision-related quality of life subscales and one additional general health item. The 11 subscales are general vision (item 2), difficulty with near vision activities (items 5, 6, 7), difficulty with distance vision activities (items 8, 9, 14), limitations in social functioning due to vision (items 11, 13), role limitations due to vision (items 17, 18), dependency on others due to vision (items 20, 23, 24), mental health symptoms due to vision (items 3, 21, 22, 25), driving difficulties (items 15c, 16, 16a), limitations with peripheral vision (item 10), limitation with color vision (item 12), and ocular pain (items 4, 19). The general health item is item 1.

Responses to individual questions are recoded to scores using the following scoring system, with a higher score representing better functionality. For example, for question 1, a score of 100 is applied for a response of “1.” The summary score for each subscale is determined by taking the average across multiple items within each corresponding subscale. For subscales calculated based on multiple questions, at least one non-missing response is required (i.e., at least one question is answered). The overall composite score is then calculated by averaging over all 11 vision-targeted subscale scores, excluding the general health score. Items or subscales that are left blank are excluded from the calculation of average scores; e.g., if any of the 11 subscale scores is missing, the overall composite score will be calculated based on the mean of the non-missing subscales.

Table 10-1 VFQ-25 Coded Values for Each Item

Items	Response Level	Coded value
1, 3, 4, 15c ^a	1	100 (best)
	2	75
	3	50
	4	25
	5 ^b	0 (worst)
2	1	100 (best)
	2	80
	3	60
	4	40
	5	20
	6	0 (worst)
5-14, 16, 16a	1	100 (best)
	2	75
	3	50
	4	25
	5	0 (worst)
	6	Missing
17-25	1	0 (worst)
	2	25
	3	50
	4	75
	5	100 (best)

a Value assigned to Item 15c also depends on the response to 15b as follows: if 15b = 1 (mainly eyesight), then 15c is set to 5 and recoded to 0; if 15b = 2 (mainly other reasons) or 3 (both eyesight and other reasons), then 15c is set to missing

b Item 15c has 4 response levels and is expanded to 5 levels when 15b = 1

11.0 SAFETY ANALYSES

Safety assessments in this study are divided into measures of ocular safety and measures of systemic safety (Protocol Section 6.1). The safety parameters will include adverse events (AEs), ocular measurements, clinical laboratory tests including immunogenicity tests, vital signs, and ECG parameters. For each safety parameter, the last non-missing assessment before the first dose of study treatment will be used as the baseline for all analyses.

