### **5.2.16        Intraocular Pressure (IOP)**

IOP measurements will be performed in both eyes at every study visit except on treatment day (Day 0), where there will be a pre- and post-injection IOP measurement in the study eye only. After the intravitreal injection, the patient will remain in the supine position and IOP will be monitored for at least 30 minutes. In the event that the intraocular pressure is 30 mmHg or above, it will be managed according to Section 5.3.2.

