Visit Windows (Days) ^a	-45 to -8	-7 to -1	0	1	7 ± 1	1 ± 7	3 ± 7	6 ± 7	9 ± 7	12 ± 30	18 ± 30
Informed Consent/Authorization	X										
Ophthalmic and Medical History	X	X	X								
Concomitant medications and procedures	X	X	X	X	X	X	X	X	X	X	X
Adverse Events review	X	X	X	X	X	X	X	X	X	X	X
Physical Examination	X										
Pregnancy Test	X	X									
Blood Sample ^d	X	X									
Electrocardiogram (ECG)	X										
Chest X-ray	X										
Visual acuity	X	X									
Full Field Sensitivity Testing (FFST)	X	X									
Object detection and discrimination	X	X									
Pupillometry (at selected sites)		X									
Ambulation		X									
Complete Ophthalmic Examination	X	X									
Intraocular Pressure (IOP)	X	X									
Spectral Domain Optical Coherence Tomography (SD-OCT)	X	X									
Color Fundus Photography and Autofluorescence		X									
Electroretinography (ERG)	X										
Visual Evoked Potentials (VEP)		X									
Quality-of-life questionnaire		X									
Study drug administration ^f											

- a Assessment administration may extend over more than one day.
- b If convenient, the Screening and Baseline visits may be combined.
- c Month 24 or early termination visit.
- d Blood samples will include hematology, chemistry and RST-001 immunogenicity testing: see Protocol [Appendix 2](#) for details.
- e IOP measurements will be performed pre- and post-injection in the study eye only. After the intravitreal injection, the patient will remain in the supine position and (IOP) intraocular pressure will be monitored for at least 30 min. In the event that the IOP is 30 mmHg or above, this will be managed according to protocol (Section 5.3.2).
- f Topical corticosteroid treatment may be given to the injected eye according to the investigator's standard of care.

Table 4-4. Study Visit Schedule: Long-term Follow-up Visits

Visit Windows (Month \pm Days)	Months											
	Clinic Visits						Teleconference Interviews					
	36 \pm 30	48 \pm 30	60 \pm 30	72 \pm 30	84 \pm 30	96 \pm 30	108 \pm 30	120 \pm 30	132 \pm 30	144 \pm 30	156 \pm 30	168 \pm 30
Concomitant medications and procedures	X	X	X	X	X	X	X	X	X	X	X	X
Adverse Events review	X	X	X	X	X	X	X	X	X	X	X	X
Visual Acuity	X	X	X	X	X							
Complete Ophthalmic Examination	X	X	X	X	X							

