Retina Periphery	Retinal Hemorrhage Retinal Tear Rhegmatogenous retinal detachment, macula center attached Rhegmatogenous retinal detachment, macula center detached Tractional retinal detachment, macula center attached [Tractional retinal detachment, macula center detached Exudative retinal detachment, macula center attached Exudative retinal detachment, macula center detached Other retinal detachment Round (Atrophic) Retinal Hole Lattice Degeneration Other	Not Applicable

^aSeverity for Vitreous flare and Vitreous Haze are included before or after ' ; ' , respectively.

The findings from both ocular biomicroscopic and ophthalmoscopy examinations with prespecified terms will be coded using MedDRA, version 21.0 or newer.

Descriptive statistics for IOP measurements and changes from the baseline values at each visit will be presented by treatment group separately for each phase.

Similarly, descriptive statistics for cup/disc ratio measurements from ophthalmoscopy examination and changes from the baseline values at each visit will be presented by treatment group separately for each phase.

The number and percent of patients with more than one grade increase from baseline for any findings will be summarized by preferred term and by treatment group separately for each phase.

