15.2 VISIT TIME WINDOWS

[Table 15.2–1](#) presents the visits assigned for efficacy and safety analyses and the corresponding range of treatment days (window) during which an actual visit may occur.

Table 15.2–1. Visit Time Windows

Derived Visit	Scheduled Visit (Target Day^a)	Window
Baseline	Day -45 to 0	Days < 0
Day 0	Treatment Visit (Day 0)	Day 0
Day 1	Post Injection Visit (Day 1)	Day 1
Day 7	Day 7 (7)	Days (2, 12)
Month 1	Month 1 (30)	Days (13, 47)
Month 3	Month 3 (91)	Days (48, 135)
Month 6	Month 6 (183)	Days (136, 230)
Month 9	Month 9 (274)	Days (231, 317)
Month 12	Month 12 (365)	Days (318, 412)
Month 18	Month 18 (548)	Days (413, 682)
Month 24	Month 24 (731)	Days (683, 778)
Month 36	Month 36 (1096)	Days (779, 1413)
Month 48	Month 48 (1461)	Days (1414, 1508)
Month 60	Month 60 (1826)	Days (1509, 2144)

Month 72	Month 72 (2192)	Days (2145, 2238)
Month 84	Month 84 (2557)	Days (2239, 2874)
End of study ^b	Final or Termination Visit	

a Relative to the date of the first dose of study treatment. Day 0 = the date of the first dose of study treatment.

b Presented in summary tables for all visit-based parameters.

If the assessment date (if the assessment date is unavailable, use visit date instead) is on or after the date of the first dose of study treatment, the study day is calculated by assessment date – date of the first dose of study treatment + 1. If the assessment date is before the date of the first dose of study treatment, the study day is calculated by assessment date – date of the first dose of study treatment. Therefore, a negative day indicates a day before the start of the study treatment.

If a patient has 2 or more visits within the same window, the last visit with a non-missing value will be used for analysis.

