15.4 REPEATED OR UNSCHEDULED ASSESSMENTS OF SAFETY PARAMETERS

If a patient has repeated assessments before the start of the first treatment, the results from the final non-missing assessment made prior to the start of the study treatment will be used as baseline. If end-of-study assessments are repeated or if unscheduled visits occur, the last non-missing Post-treatment assessment will be used as the end-of-study assessment for generating summary statistics. However, all Post-treatment assessments will be used for PCS value determinations, and all assessments will be presented in the data listings.

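### The SAP's baseline text and its visit-window table pick different baseline readings for study-eye IOP, and nothing says which one governs

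*SAP*

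**What the plan says.** Three parts of the SAP bear on the IOP baseline.

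- **Text rules.** SAP 11.0, for each safety parameter: "the last non-missing assessment before the first dose of study treatment will be used as the baseline for all analyses". SAP 15.4, for repeated pre-treatment assessments: "the results from the final non-missing assessment made prior to the start of the study treatment will be used as baseline". SAP 5.0 (visual acuity) and SAP 10.0 (efficacy) use the same principle.
- **Window table.** Table 15.2-1 in SAP 15.2 is introduced as governing both efficacy and safety analyses. Its Baseline row gives a target range of Day -45 to 0 but a window of Days < 0. Day 0 is a separate derived visit with its own window.
- **Day count.** The footnote to that table says "Day 0 = the date of the first dose of study treatment". The text below it says that, on or after the dose date, "the study day is calculated by assessment date – date of the first dose of study treatment + 1".

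On data collection, Protocol 5.2.16 has IOP measured in both eyes at every visit "except on treatment day (Day 0), where there will be a pre- and post-injection IOP measurement in the study eye only". The footnote to the SAP's own visit schedule agrees: "IOP measurements will be performed pre- and post-injection in the study eye only". After injection, IOP is monitored for at least 30 minutes, and 30 mmHg or above is the protocol's threshold for management.

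On use, SAP 11.4 says: "Descriptive statistics for IOP measurements and changes from the baseline values at each visit will be presented by treatment group separately for each phase". SAP 5.0 also lists study-eye IOP from baseline among the safety measures for the primary objective.

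**The concern.** A change-from-baseline table needs one baseline. For most assessments the text and the window table would normally agree, because little is measured on Day 0 before dosing. IOP is different: a pre-injection reading is scheduled on the treatment day itself. The text rules admit that reading and the window excludes it. The SAP gives no order of precedence, so whoever programs the table decides the baseline.

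The by-visit IOP change summary in SAP 11.4 and the from-baseline IOP measure in SAP 5.0 are exposed. With about three patients per Phase 1 dose group, a difference in one patient is visible in the group mean.

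The Day 0 row has a related problem. It would hold both pre- and post-injection readings, and the SAP does not say which of them represents Day 0.

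**Working it through.** The plan states no figure to reproduce. The check applies each rule to one scheduled IOP sequence and records which reading it selects. The dates of Day -30 for Screening and Day -5 for the Baseline visit are assumptions, chosen inside the planned ranges of -45 to -8 and -7 to -1.

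**Step 1: which reading is the baseline?**

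| Rule | Reading selected |
|---|---|
| SAP 11.0 and 15.4, last value before dosing | Day 0 pre-injection, study eye |
| Table 15.2-1 window, Days < 0 | Baseline visit (Day -5) |
| Table 15.2-1 target range, Day -45 to 0 | Admits Day 0, so disagrees with its own window |

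The first two rules differ for every patient who has both readings.

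**Step 2: effect on the change score.** Let y be the IOP at a later visit, p the Day 0 pre-injection reading and c the Baseline-visit reading. The two change scores are y - p and y - c. Their difference is (y - c) - (y - p) = p - c = d, which is the same at every visit. In a group of n patients the mean change moves by d/n if one patient is affected, and by d if all are.

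The documents do not give d. For an assumed range of 1 to 5 mmHg:

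| n | One patient affected (d/n) | All affected (d) |
|---|---|---|
| 3 | 1/3 = 0.33 to 5/3 = 1.67 mmHg | 1 to 5 mmHg |
| 6 | 1/6 = 0.17 to 5/6 = 0.83 mmHg | 1 to 5 mmHg |
| 12 | 1/12 = 0.08 to 5/12 = 0.42 mmHg | 1 to 5 mmHg |

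**Step 3: does the day count settle it?** It does not. Study day is computed from dates, so pre- and post-injection readings on Day 0 receive the same value. The formula also conflicts with the footnote:

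| Reading | Day by footnote, window | Day by +1 formula, window |
|---|---|---|
| Day 0 pre-injection | 0, Day 0 | 1, Day 1 |
| Day 0 post-injection | 0, Day 0 | 1, Day 1 |
| Day 1 visit | 1, Day 1 | 2, Day 7 (2 to 12) |
| Day 7 visit | 7, Day 7 | 8, Day 7 |
| Month 6 visit | 183, Month 6 | 184, Month 6 (136 to 230) |

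Taken literally, the formula leaves the Day 0 window empty, because no date can yield study day 0. It reports treatment-day readings as Day 1 and places the Day 1 visit in the Day 7 window. SAP 15.2 keeps the last visit with a value in a window, so the Day 1 IOP would drop out of the by-visit table whenever a Day 7 value exists. Month 6 stays in its own window. Under either count the pre-injection reading lies outside Days < 0.

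**The case against.** The best defence is that the two rules are not evenly matched. Last value before dosing is stated several times in the SAP, and the table's own target range reaches Day 0. Only the window cell is out of line, and the table assigns visits rather than defining baseline. This is a fair guide to which way to resolve the conflict. It does not remove it, because the table is declared to apply to safety analyses and contains a row named Baseline.

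The last reading before dosing is also a legitimate baseline. That stands.

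A reader might infer more than the documents support:

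- **That the Day 0 reading is distorted by posture or instrument.** Protocol 3.12 puts the injection in the operating room, and Protocol 4.8 has the patient supine immediately before administration. Neither says how the pre-injection IOP is taken. The Day 0 procedure list is partly redacted, and details sit in a manual outside these documents. Protocol 5.2.15 allows a hand-held tonometer without tying it to a visit.
- **That measuring only the study eye on Day 0 biases the comparison of eyes.** No between-eye contrast is planned. The stated IOP measures concern the study eye.
- **That a later rise would be hidden.** SAP 11.4 summarises IOP values as well as changes, and SAP 15.4 lists all assessments.
- **That a post-injection spike will be discarded.** The last-value rule in SAP 15.2 chooses between visits. It does not address several readings within one visit.
- **That the primary safety conclusion depends on this.** Protocol 11.1 and SAP 11.2 list IOP measurements without the word change. The safety criterion in SAP 5.0 is the absence of related grade 3 or greater adverse events.

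**Conclusion.** The conflict is real and unresolved within the SAP. It affects the by-visit IOP change summary and the from-baseline IOP measure in SAP 5.0. Each affected patient's change differs by d at every visit. At an assumed d of 1 to 5 mmHg, the mean change in a group of three moves by 0.33 to 1.67 mmHg with one patient affected, and by 1 to 5 mmHg with all three. That range illustrates sensitivity. It is not evidence that the two readings will differ by that much.

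The day-count contradiction is separate and does not depend on d. Applied literally, it misplaces the Day 0 and Day 1 readings.

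The analyses are descriptive, so no test, error rate or sample size is involved. Both readings are acceptable baselines, and the documents give no ground for preferring a clinic-only one. The point is worth correcting because the result would otherwise rest on an undocumented programming choice.

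**What to change.** 1. State one IOP baseline rule and apply it in SAP 11.0, 15.4 and Table 15.2-1. The simplest way is to align the Baseline row with the text rule and say explicitly that the Day 0 pre-injection reading counts. The row's target range and window should then agree.
2. Identify Day 0 IOP readings by a timepoint label, pre- or post-injection, because dates cannot separate them.
3. Reconcile the +1 study-day formula with the definition of Day 0 as the dose date, so that the Day 0 and Day 1 readings fall in the windows that bear their names.
4. For Day 0, summarise the maximum post-injection IOP and the number of patients with any reading of 30 mmHg or above. The threshold is already in the protocol. This is a reporting summary and changes no clinical rule.

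The cost is SAP and table-shell wording. The readings are already scheduled, so no new data are needed. Protocol 11.3.6 has the analysis plan finalised before database lock, so the changes should be made before then.

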11.1 ADVERSE EVENTS

Adverse events will be coded using *MedDRA*, version 21.0 or newer.

An AE will be considered a treatment-emergent adverse event (TEAE) if it was present after the first dose of study treatment or was present before the date of the first dose of study treatment and increased in severity after the first dose of study treatment. If more than 1 AE was reported before the first dose of study treatment and coded to the same preferred term, the AE with the greatest severity will be used for comparison with the AEs occurring during the reporting periods.

The number and percent of patients reporting TEAEs will be tabulated by treatment group in each phase separately during Core Study Visits and Long-term Follow-up Visits for the following categories:

- All TEAEs
- Treatment related TEAEs
- Ocular TEAEs in the study eye
- Non-ocular TEAEs
- Treatment-related ocular TEAEs
- Serious TEAEs
- Deaths
- AEs leading to study discontinuation

The above categories will also be tabulated by SOC and PT, or by PT only for ocular related categories, with the number and percentage of patients by treatment group in each phase and separately during Core Study Visits and Long-term Follow-up Visits, except for the last 3 categories.

In addition, the number and percent of patients will be tabulated by SOC, PT, and severity, or by PT and severity only for ocular related categories, with the number and percentage of patients by treatment group in each phase and separately during Core Study Visits and Long-term Follow-up Visits for the following categories:

- All TEAEs
- Treatment related TEAEs
- Ocular TEAEs in the study eye
- Non-ocular TEAEs
- Treatment-related ocular TEAEs

If more than 1 AE is coded to the same PT for the same patient, the patient will be counted only once for that PT using the greatest severity and strictest causality for the summarization by severity and causal relationship.

Separate tabular displays will be presented for patients who died, patients with SAEs, and patients with AEs leading to premature discontinuation.

